After enrollment, patients will be randomized using the "envelope method" into two equal groups of 168 patients each (a total of 336 people, including 10% who may have dropped out) and assigned to receive either Fortelyzin® or Actilyse®. Fortelyzin® will be given as single i.v. bolus over 5 - 10 seconds. Actilyse® will be administered following the instruction for use.

To compare the efficacy and safety of Fortelyzin® vs Actilyse®, patients will be monitored for 90 days after administration of the drug. During this period, patients will have 6 visits (Table 5).

Table 5. Plan of the trial

	V 1	V 2	V 3	V 4	V 5	V 6
	0	1 day	2 days	7 days	14 days	90 days
Signing Informed consent	+	–	–	–	–	–
Demographic data	+	–	–	–	–	–
Previous treatment	+	–	–	–	–	–
CT/MRI SCAN	+	+	–	+	–	–
ASPECTS	+	+	–	+	–	–
Dynamics of neurological status	–	+	+	–	–	–
Changes by organs and systems	–	+	+	+	+	–
TOAST criteria	–	–	+	–	–	–
Medical history	+	–	–	–	–	–
Measurement of vital signs	+	+	+	+	+	+
Physical examination	+	–	–	–	–	–
Concomitant diseases	+	–	–	–	–	+
NIHSS	+	+	+	+	+	+
Bartel	–	–	–	+	+	+
Rankin	+	–	+	+	+	+
Meningeal symptoms	+	+	+	+	+	–
ECG	+	–	–	+	+	–
Duplex scanning of the major arteries of the head (if necessary)	+	–	–	+	–	–
Coagulogram	+	+	+	+	+	–
Complete blood count	+	–	+	+	+	–
Biochemical blood analysis	+	–	–	+	+	–
Blood sampling for Pharmacokinetic analysis	–	+	–	–	–	–
Common urine analysis	+	–	+	+	+	–
Inclusion/Exclusion criteria	+	–	–	–	–	–
Angiography of cerebral vessels (if necessary)	+	–	–	–	–	–
Administration of Fortelyzin® or Actilyse®	–	+	–	–	–	–
Change in concomitant therapy	–	+	+	+	+	+
Registration of AE	–	+	+	+	+	+
Bleeding assessment	–	+	+	+	+	–

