9. TRIAL PROCEDURES

Visit 1 (Start of the trial)

Prior to administration of the trial drug, all patients will undergo the following procedures:

- determination of inclusion/non-inclusion criteria
- signing of Informed consent
- collection of demographic data (date of birth, sex)
- collection of medical history (duration of the underlying disease, previous therapy, allergological anamnesis, etc.)
- physical examination
- evaluation of changes by organs and systems
- assessment of neurological status using the NIHSS and modified Rankin scales (mRS)
- Duplex scanning of the major arteries of the head (if necessary)
- CT/MRI examination of the brain
- assessment of CT changes according to ASPECTS (Alberta Stroke Program Early CT Score)
- angiography of the cerebral vessels (if necessary)
- blood sampling for hematological and biochemical analyses
- coagulogram
- common urine analysis
- ECG
- assessment of the patient's compliance with the inclusion/exclusion criteria
- randomization

Assignment of individual patient identification code (IPIC)

The Investigator must ensure the anonymity of the trial subjects. The full names of all patients participated in the trial are strictly confidential.

After signing the Informed Consent Form, each patient will be assigned an Individual Patient Identification Code (IPIC) in accordance with the current legislation (Table 6).

Table 6. Individual Patient Identification Code

Permission of the Ministry of Health of the Russian Federation No.	Permission's date of issue, DD/MM/YYYY/	Serial number of the medical organization specified in the Permission	Patient's initials	Patient's date of birth, DD/MM/YYYY/	A unique number assigned to the patient by the Investigator, consisting of letters and numbers (the name of the protocol and the screening number under which the patient was included in the trial)
--	---	---	--------------------	--------------------------------------	--

The individual patient identification code (IPIC) is established by the Insurant based on the patient data provided by the Investigator. The individual patient identification code is reported by the Insurant to the Investigator for inclusion in his medical documentation. The IPIC will be reflected in the primary documentation, Case Report Form, and Patient Information Sheet with the informed consent form. The IPIC will be transmitted by the Code Registry by the Insurant to the Insurer.

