The individual identification code assigned to the patient is not subject to change.

The Investigator should maintain a separate Identification Registry containing the individual numbers, surnames, dates of birth, addresses, phone numbers, and medical records (if available). Only the initials, dates of birth, and unique patient numbers that are part of the Individual Patient Identification Code will be used in the report and trial documentation.

The randomization plan will be known by the Principal Investigator and Regulatory Authorities.

Visit 2.

- Administration of Fortelyzin® or Actilyse®.
- On Visit 2, the changes in neurological status will be recorded, as well as registration and evaluation of bleeding and adverse events based on patient complaints, data from neurological, physical, and laboratory-instrumental studies.

Table 7. Monitoring of parameters at the moment of thrombolysis

Trial parameter	Frequency of examination
BP	Every 15 minutes to 2 hours after the start of thrombolysis
Vital signs	Every 30 minutes for 6 hours
NIHSS	Every 15 minutes for 1 hour
Meningeal symptoms	Every 15 minutes for 1 hour

Table 8. Monitoring of parameters during the first day (24h) after thrombolysis

Trial parameter	Frequency of examination
BP	Every hour until the end of the day (within 24 hours)
Vital signs	Every 30 minutes to 6 hours, then every hour until the end of the day
Meningeal symptoms	Every hour for 24 hours
NIHSS	Every hour for 24 hours

- CT/MRI 24 hours after TLT or if the patient's condition worsens
- assessment of CT changes according to ASPECTS
- registration of adverse events (AE)
- assessment of bleeding

All adverse events identified should be recorded in the Case Report Form (CRF). The Investigator should report the adverse events to Roszdravnadzor within the next 24 hours. The assessment of bleeding is carried out according to the corresponding scales (see Safety assessment). Monitoring of coagulogram parameters (fibrinogen) will be carried out within 24 h from the time of Fortelyzin® or Actilyse®

administration. CT/MRI examination of the brain will be repeated 24 hours after the thrombolysis or if the patient's condition worsens.

During the visit, patients will receive treatment in accordance with the Russian Clinical Guidelines for Thrombolytic Therapy in Ischemic Stroke, 2015.

Visit 3.

- verification of the stroke subtype according to TOAST criteria
- measurement of vital signs
- physical examination

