18. STATISTICAL ANALYSIS OF RESEARCH MATERIALS

For Statistical Analysis R 3.5.1 package will be used.

Normally distributed variables will be described as mean (SD), ordinal variables as median (IQR), and categorical variables as number and percentage per category. For calculation of significant differences between proportions, we shall use the χ^2 method and for medians the Mann-Whitney U test (with a two-sided 5% level of significance). Ninety-five percent confidence intervals will be calculated for quantitative data.

The primary outcome and other continuous variables will be analyzed with a linear regression model. Binary variables will be tested using logistic regression models adjusted for the same stratification variables, p-values for the difference between treatment groups will be extracted from these models.

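### Section 18 adjusts for stratification variables that the documents never name, lists the binary primary outcome as continuous, and extracts p-values for a difference instead of testing the 16-point margin

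*Combined protocol and SAP*

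**What the plan says.** **Analysis (section 18).** Proportions are compared by chi-square at the two-sided 5% level. Confidence intervals at 95% are promised for quantitative data. The modelling paragraph then reads "The primary outcome and other continuous variables will be analyzed with a linear regression model", followed by "Binary variables will be tested using logistic regression models adjusted for the same stratification variables". P-values for the difference between arms are to be taken from these models.

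**Randomisation (sections 8 and 9).** Section 8 states that "patients will be randomized using the 'envelope method' into two equal groups of 168 patients each". Section 9 adds: "The randomization plan will be known by the Principal Investigator and Regulatory Authorities". The content of that plan is not given. The protocol summary says that randomisation takes place in the clinical centres.

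**Baseline data (section 9, Visit 1).** Collected before treatment are "assessment of neurological status using the NIHSS and modified Rankin scales (mRS"), "collection of demographic data (date of birth, sex") and "assessment of CT changes according to ASPECTS (Alberta Stroke Program Early CT Score"). Section 18 gives none of these a role.

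**Hypothesis (sections 11 and 17).** The primary endpoint is mRS 0-1 at day 90. The null hypothesis is that the Fortelyzin minus Actilyse difference in proportions is -16 points or worse.

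**The concern.** The logistic sentence refers back to stratification variables as though they had been introduced, but nothing earlier in section 18, and nothing in the randomisation text, introduces any. Whoever analyses the trial must either drop the adjustment or decide what it is. If that decision comes after outcomes are known in an open-label trial, the result is open to selection.

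Two faults in the same paragraph make this matter for the primary endpoint. A yes/no outcome is assigned to the model for continuous variables, so it is unclear whether the linear or the logistic sentence governs it. The output of either route is a p-value for a difference, whereas the trial's claim depends on excluding a deficit of 16 points. Section 18 therefore does not say which analysis decides the trial.

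**Working it through.** **1. Does the phrase have a referent?** Places where one could be:

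| Place | Content |
|---|---|
| Section 18, preceding sentence | Linear model; no covariate listed |
| Section 8 and protocol summary | Envelopes, two equal groups; no factor or block |
| Section 9, Visit 1 | A randomisation plan exists; content not given |
| Section 17 | 1:1 allocation; no strata |

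None names a variable.

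**2. The plan's own sample size.** Inputs from section 17: 54.8% in both arms, margin 0.16, two-sided 5% (one-sided 2.5%), power 80%.

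n = (1.960 + 0.842)² × 2 × 0.548 × 0.452 / 0.16² = 151.9, so 152 per group, as stated. Adding 10% gives 152 × 1.10 = 167.2, so 168. Dividing by 0.90 would give 169, which is immaterial. The calculation is unadjusted and does not depend on the missing covariates.

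**3. What a p-value for a difference can and cannot show.** At 152 per arm the standard error is √(2 × 0.548 × 0.452 / 152) = 0.0571, and 1.96 × 0.0571 = 0.112.
- A difference is significant at 5% when the estimate is beyond ±11.2 points.
- Non-inferiority is shown when the estimate is above -16 + 11.2 = -4.8 points.
- An estimate between -11.2 and -4.8 points gives a non-significant difference and also fails non-inferiority. The p-value does not separate this case from success.

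**4. What defined adjustment would gain.** If baseline covariates explain a share R² of the outcome variance, the variance of the risk difference is multiplied by about (1 - R²). Power is then Φ(0.16 / (0.0571 × √(1 - R²)) - 1.96). The documents give no prognostic strengths, so these are assumptions: log-odds 0.10 to 0.20 per NIHSS point, 0.02 to 0.03 per year of age, age SD 10, and three possible NIHSS spreads.

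| NIHSS spread (assumed) | Variance reduction | Power at 152 per arm |
|---|---|---|
| SD 3 | 3-9% | 81-84% |
| SD 4.3 | 5-15% | 82-86% |
| Uniform over 5-25 | 8-24% | 83-90% |

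Without adjustment, power is 80.0%. A simulation of 4,000 trials per scenario, with one covariate and a standardised logistic model, agrees with the formula: at R² of about 0.06 power went from 80.1% to 81.8%, and at about 0.17 from 80.5% to 86.8%.

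**5. What an open covariate choice could do.** In simulation with the true difference at -16 points, pre-specified adjustment for NIHSS and age kept the false non-inferiority rate at 2.2-2.5%. Taking the most favourable of the 16 subsets of four covariates (NIHSS, age, sex, onset time) raised it from 2.5% to 3.4-3.9%. This is a worst case under assumed effects. It shows what the wording leaves possible and does not predict conduct.

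**The case against.** Several points against the concern have force.

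- **A reader might infer that the randomisation is known to be unstratified.** The documents do not show that. A randomisation plan exists whose content is not given, and randomising in the centres may mean a set of envelopes per centre. The supportable statement is that no factor is described. If centre was used, the phrase has a meaning, but the text still does not state it.
- **A reader might infer that the binary outcomes cannot be analysed.** Only the adjusted model is undefined. The chi-square test and an unadjusted logistic model can be run, and the sample size stands.
- **A reader might infer that chance imbalance in stroke severity biases the result.** Under randomisation, the unadjusted confidence interval already allows for chance imbalance. Adjustment buys precision and does not rescue an invalid comparison.
- **Linear regression on a 0/1 outcome can be defended**, because its treatment coefficient is a risk difference. That would help if the section said so. Instead it lists the outcome as continuous, names no covariates, and asks for p-values rather than a confidence limit.
- **Onset-to-treatment time may look like an obvious covariate.** It is not listed at Visit 1, and it is fixed only after open-label randomisation, since the drug is given at Visit 2. Allocation could influence it.
- **The size of the gain rests on assumptions.** This is correct, and the range above is wide for that reason.

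These points limit the claim. They do not supply the missing variables or the missing test against the margin.

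**Conclusion.** The point holds in limited form. Section 18 promises an adjusted analysis without saying for what, places the binary primary outcome under the model for continuous variables, and extracts p-values that do not test the hypothesis of section 17. The consequences are loss of pre-specification in an open-label trial, loss of the precision that baseline data already collected would give, and no stated link from the model to the margin.

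The precision at stake is a variance reduction of about 3-24%, or power of about 81-90% instead of 80% at 152 per arm. This rests on the assumed coefficients, age SD and NIHSS spreads given above. That the phrase has no referent, that the outcome is misclassified, and that the p-value does not test the margin all follow from the text and need no assumption. The change should be made before any comparison of outcomes by arm. It gives no reason to question the 336 patients or to call an unadjusted comparison biased.

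**What to change.** In section 18:

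1. Replace the reference to stratification variables with: baseline NIHSS and age (Visit 1), plus any factor actually used in randomisation, such as centre. State in section 8 which factors, if any, the randomisation used.
2. Remove the primary outcome from the linear-regression sentence and state that mRS 0-1 at day 90 is analysed as binary.
3. Make the primary estimate the Fortelyzin minus Actilyse risk difference, obtained from the logistic model by standardisation over all analysed patients. Conclude non-inferiority if its lower two-sided 95% confidence limit lies above -16 points.
4. Report the unadjusted risk difference with its 95% interval as a sensitivity analysis.
5. Do not adjust for onset-to-treatment time. Onset-to-randomisation time may be added if it is recorded.

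The cost is wording only. NIHSS and date of birth are already collected at Visit 1, and the sample size does not change.

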Number of patients	Sex, m/f	Average age, Min-max (years old)	Number of patients > 75 years old	Localization of infarction		Average door-to-needle time Min-max (min)
				anterior	posterior	
1531	924 / 607	65 32-89	322	789	742	176 40-720

The time from the onset of symptoms of myocardial infarction to the administration of Fortelyzin® was 176 min., which is 10% less than in 40 regions of the Russian Federation implementing the Vascular Program, but 50% higher than in the studies carried out by Tomsk Research Institute of Cardiology and almost 2 times higher than in the STREAM trial.

ECG evidence of myocardial reperfusion was observed in 1,148 patients out of 1,531, which was 75%. Angiography confirmed coronary reperfusion in 141 out of 179 patients (79%), and TIMI 3 was observed in 104 out of 179 patients, which was 58%.

Hemorrhagic stroke occurred in 7 out of 1,531 patients (0.46%), with 2 patients older than 75 years. The 30-day mortality rate was 5.3%. Major non-cerebral bleeding was observed in 3.7%, of which: 1.6% required blood transfusion; minor bleeding from the puncture sites was noted in 10.7% of patients (Table 4).

Table 4. Evaluation of the efficacy and safety of Fortelyzin®

Signs of reperfusion (reduction in the ST elevation by 50 %) (N = 1531)	TIMI (N = 177)			intracranial hemorrhage	Death within 30 days	Major non-cerebral bleeding	Bleeding required blood transfusion	Minor bleeding
	3	2	3 + 2					
1148 74,9 %	104 58 %	37 21 %	141 79 %	7 0,46 % among them 2 > 75 years old	81 5,3 %	56 3,7 %	25 1,6 %	165 10,7 %

These data on the efficacy and safety of Fortelyzin®, based on the monitoring of 1,531 STEMI patients, indicate the results comparable to thrombolytics Actilyse® and Metalyse®.

Since 2015, the original drug Fortelyzin® (a recombinant protein containing the amino acid sequence of staphylokinase) has been included by the RF Government in the updated list of vital and essential medications for medical use.

Background for the dose of Fortelyzin® in patients with ischemic stroke

To find a safe and effective dose of Fortelyzin® for AIS patients, *in vitro* and *in vivo* experiments were performed.

At the first stage, the *in vitro* studies of molecular mechanisms of fibrinolysis of the fibrin-selective thrombolytics used in the treatment of AIS patients were carried out to compare Actilyse® and Purolase with Fortelyzin® used in the treatment of AMI.

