12. SAFETY ASSESSMENT

- Safety endpoint - overall mortality on day 90.
- Safety endpoint - hemorrhagic transformation (all cases).
- Safety endpoint - symptomatic hemorrhagic transformation (as defined by ECASS III).
- The number of SAE and AE by organs and systems.

The assessment of safety is based on the number and severity of adverse events that may occur in the course of the trial. The drug is considered as well tolerated if no severe adverse events are registered during the trial (fatal outcome or life-threatening conditions of the patient), which, according to the Investigator, may be associated with the application of the drug studied.

Adverse events

Adverse event (AE) is any unfavorable medical occurrence in a patient or clinical trial subject administered a pharmaceutical product, which may not have a causal relationship with its use. Thus, an adverse event can be any adverse symptom (including deviation of the laboratory value from the norm), a complaint, or a disease, the time of occurrence of which does not exclude a causal relationship with the use of the medicinal product, regardless of the presence or absence of such communication.

Information about adverse events should be collected at each visit by interviewing the patient, as well as during physical examination and evaluation of laboratory and instrumental data. All adverse events that occur during the trial should be evaluated and documented.

When registering an adverse event, the following information should be reflected, if possible:

- the exact time of AE occurrence и разрешения
- the nature of the adverse event
- severity (mild, moderate, severe)
- causal relationship with the study drug
- whether the adverse event is serious
- actions taken (whether AE required any therapeutic measures)
- outcome

Adverse Event Grading:

- **Mild:** the presence of signs or symptoms that do not affect daily activities.
- **Moderate:** event has sufficient intensity to interfere with daily activities.
- **Severe:** inability to work or perform daily activities.

The connection between the development of an adverse event and the use of the study drug is determined by the WHO scale:

- **Certain:** Clinical manifestations of unforeseen adverse reaction (UAR), laboratory findings deviations that occur during the period of drug administration, can not be explained by the presence of existing diseases and the influence of other factors.

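### Section 18 gives two tests for binary outcomes, no order of priority and no rule for sparse events; a default Wald p-value from the logistic model would be about 0.99 whenever one arm has no event.

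*Combined protocol and SAP*

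**What the plan says.** Section 18 is the whole analysis plan, and it names two procedures for binary data.

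- For proportions, "we shall use the χ^2 method and for medians the Mann-Whitney U test (with a two-sided 5% level of significance". Whether a continuity correction applies is not stated.
- "Binary variables will be tested using logistic regression models adjusted for the same stratification variables", and "p-values for the difference between treatment groups will be extracted from these models". Whether these are Wald, likelihood-ratio or score p-values is not stated. The stratification variables are not named anywhere, and the envelope randomisation in Section 8 describes no strata.

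On software: "For Statistical Analysis R 3.5.1 package will be used". Confidence intervals are promised for quantitative data only. There is no minimum event count, exact test or penalised method.

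Section 12 lists the safety outcomes these rules must serve: 90-day mortality, all haemorrhagic transformation, "Safety endpoint - symptomatic hemorrhagic transformation (as defined by ECASS III"), and "The number of SAE and AE by organs and systems". Section 8 puts 168 patients in each arm.

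**The concern.** Two gaps combine.

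First, when one arm has no event, the maximum-likelihood log odds ratio for treatment is infinite. The software stops at a large estimate with a far larger standard error, so their ratio is close to zero and the Wald p is close to 1, however many events the other arm has. Baseline covariates do not remove separation by treatment.

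Second, with few events the logistic and chi-square p-values can differ enough to straddle 5%, and the plan does not say which one is reported. Chi-square is itself doubtful there: with equal arms, the expected count falls below 5 once the total is under 10 events.

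Safety is one of the two objectives in Section 6. Followed literally with default output, the plan could attach a p-value near 1 to a marked imbalance in a rare harm, in either direction.

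**Working it through.** **Arm size.** Section 17 uses 54.8% in both arms, a margin of 16 points, two-sided 5% and 80% power:

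n = (1.960 + 0.8416)² / 0.16² × 2 × 0.548 × 0.452 = 7.849 / 0.0256 × 0.4954 = 151.9, so 152 per arm, as stated. Then 152 × 1.10 = 167.2, so 168 per arm and 336 in total. I use 168; at 152 the results below hardly change.

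**Tests.** The logistic model has treatment only, because the covariates are unnamed, and is fitted with R's default glm settings. LR is the likelihood-ratio p from the same model.

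| Events (of 168 v 168) | Wald | LR | Chi-square | Chi-square, Yates | Fisher |
|---|---|---|---|---|---|
| 0 v 5 | 0.994 | 0.008 | 0.024 | 0.071 | 0.061 |
| 0 v 6 | 0.994 | 0.004 | 0.013 | 0.039 | 0.030 |
| 0 v 8 | 0.993 | 0.0008 | 0.004 | 0.012 | 0.007 |
| 1 v 7 | 0.065 | 0.023 | 0.032 | 0.074 | 0.067 |
| 3 v 10 | 0.062 | 0.042 | 0.048 | 0.090 | 0.086 |

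Three of these by hand:

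- 0 v 6, Wald: log odds ratio 18.3, SE 2255, z = 18.3 / 2255 = 0.008, p = 0.994.
- 0 v 8, chi-square: 336 × (168 × 8)² / (168 × 168 × 8 × 328) = 8.20, p = 0.004.
- 1 v 7, Wald: ln[(7 × 167) / (1 × 161)] = 1.98; SE = √(1 + 1/7 + 1/167 + 1/161) = 1.07; z = 1.84, p = 0.065. Chi-square: 336 × (1 × 161 − 7 × 167)² / (168 × 168 × 8 × 328) = 4.61, p = 0.032, with an expected count of 4 per arm.

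**How often one arm is empty.** With the same rate r in both arms, q = (1 − r)^168 and P(exactly one arm empty) = 2q(1 − q).

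| Assumed rate | One given arm empty | Exactly one arm empty |
|---|---|---|
| 0.46% | 46% | 50% |
| 1% | 18% | 30% |
| 2% | 3.4% | 6.5% |
| 3% | 0.6% | 1.2% |
| 6% | 0.003% | 0.006% |

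The 0.46% is the haemorrhagic stroke rate in STEMI patients given the study drug (Section 2, 7 of 1,531). It is a different disease and serves only as the low end of an assumed range. The 6% is the low end of the haemorrhagic transformation range quoted for alteplase in Section 1 (6–23.8%). Section 1 also quotes 18.2% for 3-month mortality.

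**Rejection rates by exact enumeration, 168 per arm, assumed true rates.**

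| True rates | Wald | Chi-square, uncorrected | Fisher |
|---|---|---|---|
| 0.5% v 3% | 5% | 42% | 22% |
| 0.5% v 5% | 28% | 77% | 64% |
| 2% v 6% | 36% | 47% | 35% |
| 3% v 10% | 74% | 76% | 69% |
| 2% v 2% (size) | 0.6% | 4.5% | 1.4% |

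Wald and uncorrected chi-square reach different decisions in 37% of trials at 0.5% v 3%, but in only 1.4% at 10% v 18.2%.

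**The case against.** Several points on the other side have force.

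- **Wald is never named.** A reader might infer that the stated test itself fails. The text supports only a conditional claim: R's default coefficient table prints Wald p-values, but the likelihood-ratio p from the same model is 0.0008 for 0 v 8. This stands. The plan does not require the likelihood-ratio version, however, and that version is liberal here: its actual size is about 9% at 1% v 1% and 8% at 2% v 2%.
- **Sparsity is assumed.** A reader might infer that the safety endpoints as a whole will be sparse. The only stroke rates in the documents are for all haemorrhagic transformation and mortality, and at those rates an empty arm is practically excluded. This stands and limits the point to the remaining outcomes.
- **An empty arm is not yet a wrong conclusion.** The other arm must also have enough events for a valid test to reject, which for Fisher means six or more. At 0 v 5 Fisher is also above 5%.
- **Safety does not rest on p-values alone.** Section 12 assesses safety by the number and severity of events, Section 18 gives counts and percentages, and Section 20 requires discussion of adverse events. A 0 v 8 split would be visible. What remains is a misleading p-value beside it.
- **The two tests may be meant as unadjusted and adjusted analyses**, with the model governing treatment comparisons. That is a fair reading, but Section 18 does not state it. The documents do not show an intention to choose between tests after seeing the data; they only leave the choice open.

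**Conclusion.** The point holds as a gap in Section 18 for sparse binary safety outcomes. Two tests are prescribed without priority, and nothing covers an empty arm. On the assumption that the reported value is R's default Wald p, it is about 0.99 for any split with an empty arm, including 0 v 8, where Fisher gives 0.007 and chi-square 0.004. Without an empty arm, 1 v 7 and 3 v 10 fall on opposite sides of 5% under Wald and uncorrected chi-square.

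The scope is AE/SAE by organ system and possibly symptomatic haemorrhagic transformation. How often the problem would arise depends on event rates that the documents do not give for stroke: it is frequent near 0.5–1%, uncommon at 2–3% and negligible at 6%. Mortality, all haemorrhagic transformation and the primary endpoint are outside the breakdown. For them the duplicate prescription is untidy but rarely changes the decision.

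The fit here has treatment only; adjustment would change the digits but not the failure. The change should be made, but this is not a defect in the trial's main efficacy conclusion.

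**What to change.** Amend Section 18 before database lock:

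1. Name one governing test for each binary endpoint. Where a model is used, name its covariates and the type of p-value.
2. For AE/SAE by organ system and symptomatic haemorrhagic transformation, count patients with at least one event and report the risk difference with a score-type 95% interval, for example Miettinen–Nurminen.
3. For these outcomes replace the Wald p with one prespecified method that stays valid with an empty arm: an exact unconditional test such as Boschloo's, Fisher's test, or Firth-penalised logistic regression. Remove the parallel chi-square prescription for them.
4. Keep logistic regression for the common binary outcomes.
5. State that a non-significant safety test is not evidence of equal safety.

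The cost is wording only, with no extra patients, visits or data. The statistical price is conservatism: Fisher's actual size is about 1.4% at 2% v 2%, and it gains no power over Wald once the lower rate is about 2% or more (35% v 36% at 2% v 6%). The interval should therefore carry the interpretation.
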